3.2 Responsibility for Analyses/In-House Blinding

This trial will be conducted as a double-blind trial under in-house blinding procedures.

The statistical analysis of the data obtained from this trial will be the responsibility of the Clinical Biostatistics department of the Sponsor.

The Clinical Biostatistics department will generate the randomized allocation schedules for assignment of study treatment and selection of immunogenicity sub-study participants as described in Section 7.3 of the V160-002 protocol. Randomization will be implemented using IRT.

An external statistician and scientific programmer will be identified and will comprise the unblinded team. This team will be unblinded on a participant-level. They will not be involved in any discussions regarding modifications to the protocol, statistical methods, identification of protocol deviations, or data validation efforts at any time during the trial.

This trial has one planned IA, and its key aspects are described in Section 3.7 of this sSAP. The eDMC will serve as the primary reviewer of the results of the IA. Treatment-level results of the IA will be provided by the external unblinded statistician to the eDMC. The eDMC will make recommendations relating to trial discontinuation or modification to an Executive Oversight Committee (EOC) (see Appendix 1) of the Sponsor. If the eDMC recommends modifications to the design of the protocol or discontinuation of the trial, the EOC may be unblinded to results at the treatment level in order to act on these recommendations. If necessary, limited additional Sponsor personnel may be unblinded to the treatment level results of the IA in order to act on the recommendations of the eDMC. The extent to which individuals are unblinded with respect to results of IA will be documented by the external unblinded statistician. Additional logistical details will be provided in the eDMC Charter.

Upon reaching the milestone when definitive disposition of the primary and secondary efficacy hypotheses has been reached:

- A database lock will be executed.
- All Sponsor personnel who are members of the study team and the V160 program team will be unblinded and a clinical study report will be written.
- If this milestone is reached at or beyond study Year 3, or if the outcome in this milestone is failure of the test of the primary efficacy hypothesis, then the study investigators and participants will be unblinded upon completion of the clinical study report.

Definitive disposition of the primary and secondary hypotheses is reached when one of the following study outcomes occur:

1. Test of the primary efficacy hypothesis fails.
2. Tests of both the primary and secondary efficacy hypotheses succeed.
3. Test of the primary efficacy hypothesis succeeds but the test of the secondary efficacy hypothesis fails.

If at least the primary efficacy hypothesis is successfully demonstrated prior to reaching study Year 3, the study may continue to follow participants up to study Year 3 in order to continue to accumulate more information relating to vaccine efficacy against CMVi and cCMVi. Under this scenario, study investigators and participants will remain blinded during the continuing follow-up for CMVi and cCMVi information. Upon reaching the third year of the study:

- A database lock will be executed.
- An end-of-study clinical report will be written.
- The study investigators and participants will be unblinded upon completion of the end-of-study clinical report.

For the purpose of external reporting of study results in clinical trial registries (eg, EudraCT and Clinicaltrials.gov), the end-of-study milestone corresponds to the last data generated date, which is the date when all study efficacy, immunogenicity, and safety data are available and ready for database lock execution.

3.3 Hypotheses/Estimation

Objectives and hypotheses of the study are stated in Section 4 of the V160-002 protocol.

3.4 Analysis Endpoints

The efficacy, immunogenicity, and safety endpoints that will be evaluated are listed below.

3.4.1 Efficacy Endpoints

The efficacy endpoint that will be used to evaluate VE and test the primary and secondary efficacy hypotheses is the number of participants with primary CMVi, described in Section 4 and Section 5.4.1 of the V160-002 protocol.

CMVi is defined as detection of CMV DNA by PCR in urine or saliva samples.

As stated in Section 4 of the V160-002 protocol, in the evaluation of the primary and secondary efficacy hypotheses, cases of CMVi will be counted starting after the last dose of the assigned vaccination regimen. As stated in Section 3.5.1, the primary and secondary efficacy hypothesis will be evaluated on the PPE population, where eligibility includes being PCR negative post Day 1 through Month 7. Thus, CMVi cases that will be included in the PPE testing of the primary and secondary efficacy hypothesis are those that occurred after Month 7.

3.4.2 Immunogenicity Endpoints

All immunogenicity endpoints in this study are exploratory endpoints and are listed below.

- GMTs based on the NAb and the IgG ELISA assays at Day 1, Months 7, 12, 24, and 36.
- GMc of SFC/10⁶ PBMCs based on the ELISPOT assay Day 1, Months 6, 7, 12, and 24.

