| Treatment Groups | 
3 treatment groups, 1:1:1 randomization as follows:
 
• Active treatment group will receive 3 doses of vaccine V160 (100 Units/0.5 mL dose with Merck aluminum phosphate adjuvant [MAPA], 4°C stable formulation) administered intramuscularly (IM) according to a Day 1, Month 2, Month 6 schedule• Active treatment group will receive 2 doses of vaccine V160 (100 Units/0.5 mL dose with MAPA, 4°C stable formulation) administered IM according to a Day 1 (V160), Month 2 (placebo-saline solution), Month 6 (V160) schedule• A control group will receive 3 doses of placebo (saline solution) administered IM according to a Day 1, Month 2, Month 6 schedule |
| Duration of Participation | A participant may be in the trial for up to approximately 3 years, depending on when they are enrolled. Because this is an endpoint driven study, participation times will vary depending on when the participant is enrolled (subjects will be enrolled over an 18- month period and the study is planned to be a 3- year trial overall, based on reaching the primary endpoint). |

Study governance considerations are outlined in Appendix 1. A list of abbreviations used in this document can be found in Appendix 6.

2. Schedule of Activities (SoA)

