| Scheduled Day | 365 | 548 | 731 | 914 | 1096 | | Study closeout activities will be conducted at the participant's closest visit to the end of the study. Close out activities must be completed in the event of early discontinuation. Since the study completion is driven by the primary endpoint (i.e., number of events), the number of visits will depend on the timing of event accrual. |
| Scheduling Window | ± 28 days | ± 28 days | ± 28 days | ± 28 days | ± 90 days | | |
| Reminder contact for urine/saliva self-collection and pregnancy status | | | | | | X | |
| Deaths and SAEs monitoring | X | X | X | X | X | | |
| Participants NOT included in the Detailed Immunogenicity sub-study: Serum for NABs and IgG ELISA antibodies | X | | X | | X | | |
| Detailed Immunogenicity sub-study participants only: Serum for NABs and IgG ELISA antibodies Blood for CMV IFN- γ ELISPOT (PBMCs) | X | | X | | X | | |
| Urine and saliva sample for CMV | collected monthly | | | | | | Self-collected by participant starting at Day 1 (prior to vaccination) and then continue monthly through \approx Month 36 or beyond, depending on event accrual |

SAE = serious adverse event; NABs = neutralizing antibodies; IgG = immunoglobulin G; ELISA = Enzyme-linked immunosorbent assay; ELISPOT = Enzyme-linked immunosorbent spot; PBMC = peripheral blood mononuclear cell; IFN- γ = Interferon gamma

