| 
 To assess and compare the kinetics of humoral immune response induced by 2-dose and 3-dose regimens of V160 To assess and compare the kinetics of CMI response induced by 2-dose and 3-dose regimens of V160 in a subset of study participants^b To evaluate the incidence of cCMVi in infants born to recipients of 2-dose and 3-dose regimens of V160 compared to placebo, during the follow-up period after the last dose of vaccine or placebo To follow the outcomes of infants diagnosed with cCMVi in the study To explore potential correlations between humoral and CMI response to 2-dose and 3-dose regimens of V160 and efficacy of 2-dose and 3-dose regimens of V160 against CMVi | 
 Percent of participants who seroconvert based on the NAb and IgG ELISA assays from CMV seronegative at Day 1 to CMV seropositive at Month 7^a Seropositivity based on the NAb and IgG ELISA assays at Day 1, Months 6, 7^a, 12, 24, and 36 GMT based on the NAb and the IgG ELISA assays at Day 1, Months 6, 7^a, 12, 24, and 36 Geometric mean count (GMc) of spot forming cells (SFC) per million PBMCs (SFC/10⁶ PBMCs) based on the ELISPOT assay at Day 1, Months 6, 7^a, 12, 24 and 36 Incidence of cCMVi cases in the V160 2-dose, V160 3-dose, and placebo groups during the follow-up period after the last dose of vaccine or placebo Hearing, vision, and neurological outcomes of infants diagnosed with cCMVi over 3 years Immune responses in participants in the 2-dose and 3-dose vaccine groups with and without CMVi during the follow-up period after the last dose of V160 |

^a Month 7 is the time point corresponding to 1 month following last dose of the 2-dose and 3-dose regimen of V160

^b In Detailed Immunogenicity sub-study participants only (N≈360).

cCMVi = Congenital CMV infection; CMV = Cytomegalovirus; CMVi = CMV infection;

DNA = Deoxyribonucleic acid; ELISA = Enzyme-linked immunosorbent assay

ELISPOT = Enzyme-linked immunosorbent spot; IgG = Immunoglobulin G

NAb = Neutralizing antibody

PCR = Polymerase chain reaction; PBMC = Peripheral blood mononuclear cells

SFC = Spot forming cells

5. Study Design

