- Starting at the time when the facility that can process blood samples for PBMCs near a particular sub-study site is validated, study sites near the facility become a sub-study site subject to the capacity of the facility. Study participants randomized into the study by this particular sub-study site will become participants in the Detailed Immunogenicity sub-study. A site may choose to withdraw from participation in the sub-study after approval from the Sponsor. Participants of the Detailed Immunogenicity sub-study will be recruited in this manner until approximately 360 sub-study participants (or as many as are operationally feasible) across all sub-study sites have been enrolled.
 - Sites may randomize participants into the study prior to the time the PBMC blood sample processing facility is validated; however, these participants will not be included in the Detailed Immunogenicity sub-study.
- Additional study participants enrolled by sub-study sites over and above 360 sub-study participants will not be enrolled in the sub-study.

In order to increase the likelihood that approximately 360 participants enrolled into the study by sub-study sites are allocated approximately equally into the 3 treatment arms, two allocation schedules will be generated; one for use by non-sub-study sites and another for use by sub-study sites.

Randomization will stop when \approx 2100 participants have been randomized into the study.

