3.6.2 Statistical Methods for Immunogenicity Analyses

Within a vaccination group, GMT and the corresponding 95% CI will be derived by taking the anti-logarithm of the mean of the log-transformed antibody titers and its corresponding 95% CI (calculated based on the t-distribution). Antibody titers reported as less than the lower limit of quantitation (LLOQ) of the relevant assay will be replaced by the half of the LLOQ in the log-transformation of antibody titers.

Geometric mean concentration (GMC) of ELISPOT measures and the corresponding 95% CI will be calculated similar to the calculations of GMT and its corresponding 95% CI.

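### On the planned timeline the Month 24 and Month 36 antibody GMTs come from earlier enrollees than the Month 7 GMT, so the within-arm time trend needs a paired summary

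*Combined protocol and SAP*

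**What the plan says.** Protocol Section 4 sets an exploratory objective: "To assess and compare the kinetics of humoral immune response induced by 2-dose and 3-dose regimens of V160". The matching sSAP endpoint (3.4.2) is "GMTs based on the NAb and the IgG ELISA assays at Day 1, Months 7, 12, 24, and 36".

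The method in sSAP 3.6.2 is one GMT per arm per visit: "Within a vaccination group, GMT and the corresponding 95% CI will be derived by taking the anti-logarithm of the mean of the log-transformed antibody titers", with a t-based 95% CI. Neither a change from an earlier visit nor a longitudinal model is specified. The per-protocol immunogenicity (PPI) population (sSAP 3.5.2) requires an in-window Month 7 serum sample and sets no condition for later visits.

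On timing, the synopsis states that "subjects will be enrolled over an 18- month period and the study is planned to be a 3- year trial overall" and that "A participant may be in the trial for up to approximately 3 years, depending on when they are enrolled". The 3 years are counted from the first participant's consent to the last participant's last contact. The follow-up visits in SoA 2.2 are "Scheduled Day | 365 | 548 | 731 | 914 | 1096", with windows of ±28 days, except ±90 days at Month 36. The SoA adds that "the number of visits will depend on the timing of event accrual", and that close-out takes place at the scheduled visit nearest the end of the study.

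**The concern.** A series of GMTs at Months 7, 12, 24 and 36 will be read as the course of antibody in one group of women. With staggered entry and a common study end, it is not one group. Only women who entered early can contribute late samples, and the Month 7 GMT includes everyone else as well.

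If titre or decay is related to entry date, the drop between visits is partly a change of population. Persistence is part of the design's logic: Section 5.5.1 gives the Month 6 dose the role of establishing lasting immunogenicity.

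The sSAP does handle staggered entry elsewhere. In the sampling-compliance formula (3.11.2), the number of expected visits depends on when a woman entered and when the study ends. The GMT method has no matching provision.

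**Working it through.** **Inputs.** 700 per arm; 18 months of enrolment (548 days); study end at 3 years (Day 1096 from first entry); Month 24 at Day 731, window opening Day 703; Month 36 at Day 1096, window opening Day 1006; loss of 5 to 10% per year and PPE ineligibility of 2 to 5% (sSAP 3.9.1.1). Even entry is my assumption; the documents give no enrolment curve.

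**1. Does the 3-year length follow from the plan's own assumptions?** The sSAP projects 24 cases in about 3 years. Let h be the infection hazard from 2% (placebo) or 0.3% (vaccine) per year, λ the loss hazard, q the ineligible share, and u the entry month. With counting from Month 7, expected cases per arm by month T are

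700(1 − q) × average over u of h·exp(−7λ/12)·[1 − exp(−(λ + h)(T − u − 7)/12)]/(λ + h).

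Summed over the two arms, this gives 21.7 to 24.2 cases at 36 months, with 24 reached at 35.8 to 38.3 months. The 3-year projection reproduces, so it is a fair base case.

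**2. Share reaching each visit.** Share = (study end day − visit day)/548, capped at 100%.

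| Visit | On target day | At window opening |
|---|---|---|
| Months 7 and 12 | 100% | 100% |
| Month 24 | (1096 − 731)/548 = 66.6% | (1096 − 703)/548 = 71.7% |
| Month 36 | (1096 − 1096)/548 = 0% | (1096 − 1006)/548 = 16.4% |

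The close-out rule does not help. The midpoint between Months 30 and 36 is (914 + 1096)/2 = Day 1005, practically the same cut-off.

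**3. Numbers per arm after loss of 5 to 10% per year.**
- Month 7: 700 × 0.95^(7/12) = 679, down to 700 × 0.90^(7/12) = 658.
- Month 24: 700 × 0.717 × 0.95^(703/365.25) = 454, down to 410 at 10% loss.
- Month 36: 700 × 0.164 × 0.95^(1006/365.25) = 100, down to 86 at 10% loss. After 2 to 5% PPE exclusion this is about 82 to 98.

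**4. Sensitivity of the Month 36 share (window opening, before dropout).**

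| Scenario | Share |
|---|---|
| Even entry, study ends at 33 months | 0% |
| Even entry, 38.6 months | 31% |
| Even entry, 39 months | 33% |
| Even entry, 42 months | 50% |
| Even entry, 48 months | 83% |
| 36 months, entry ramping up, F(t) = (t/18)^2 to (t/18)^1.5 | 3 to 7% |
| 36 months, entry front-loaded, F(t) = (t/18)^0.75 to (t/18)^0.5 | 26 to 41% |

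With even entry, every woman reaches Month 36 only if the study runs to about 54 months.

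**The case against.** The strongest reply is that the study is event-driven. Section 5.1 ties its duration to case accrual, the SoA allows sampling beyond Month 36, and sSAP 3.2 provides for a result at or after Year 3. This stands. A reader might take one in six as a ceiling, but it is one scenario. The limit of follow-up to Year 3 applies only after an early success. The sSAP (2.1) also reports accrual above the anticipated placebo incidence, and actual enrolment is not in the documents.

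A second reply is that the objective compares regimens, and truncation by entry date falls alike on arms randomised 1:1:1. This also stands: a reader might infer a biased arm comparison at Month 36, but the loss there is one of precision.

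Third, no passage gives the order in which sites opened or says that titre varies with entry date, region or race. A reader might infer a shift in site or race mix. That is a possibility, not a demonstrated bias.

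A reader might also point to the sub-study, since of women randomised before a PBMC facility is validated the protocol says "these participants will not be included in the Detailed Immunogenicity sub-study". That does not bear on these GMTs: Month 36 serum is drawn from all participants, and the sSAP ELISPOT endpoint stops at Month 24.

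Finally, variable follow-up is disclosed and the endpoint is exploratory. Both are true, but disclosure in the SoA does not give the reader a like-for-like time trend.

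**Conclusion.** The point holds for the within-arm trend only. On the planned 36 months with even entry, the later GMTs rest on about 67 to 72% of participants at Month 24 and about 16% at Month 36, before dropout, against all of them at Month 7. Other durations and entry patterns change these shares considerably, as tabulated. The method in sSAP 3.6.2 gives no way to separate decay from the change of population. How large the distortion is cannot be stated, because it depends on a relation between entry date and titre that the documents do not describe.

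It might seem natural to treat Month 24 as the last time point that describes the whole study population. The same arithmetic argues against that: 28 to 33% are already cut off there by entry date.

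This is a cheap improvement to an exploratory analysis. It does not affect the efficacy hypotheses.

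**What to change.** In sSAP 3.6.2, add for Months 12, 24 and 36 the within-participant geometric mean fold change from Month 7 with a t-based 95% CI on the log scale. Calculate it in PPI participants with both samples, using the existing rule for titres below the LLOQ. Beside each later GMT, report n and the Month 7 GMT of that same subset. Label the Month 24 and Month 36 results as describing participants enrolled early enough to reach those visits.

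The paired change compares each woman with herself, so a change of population cannot enter it. It can also be more precise. With common log-titre variance σ² and within-woman correlation ρ, the paired change in n women has variance 2σ²(1 − ρ)/n. The difference between the later GMT (n women) and the full Month 7 GMT (N women, including those n) has variance σ²[1/n + (1 − 2ρ)/N] on the log scale. The paired version is smaller when ρ exceeds 0.5; the documents give no value for ρ.

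All the samples are already scheduled, and Section 1 of the sSAP allows exploratory analyses to be changed there before unblinding. The cost is sSAP wording, one extra table column and a narrower statement about Month 36.

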3.4.3 Safety Endpoints

As specified in Sections 4 and 5.4.1.3 of the V160-002 protocol and Section 3.6.3 of this sSAP, the endpoints that will be used to assess the safety and tolerability of 2-dose and 3-dose regimens of V160 include the following:

- Number of participants experiencing solicited injection site AEs within Days 1 through 5 after each vaccination visit; solicited systemic AEs (including tiredness, muscle pain, headache, and joint pain); and vaccine-related systemic AEs, SAEs, and elevated temperatures within Days 1 through 14 after each vaccination visit
- Incidence of any SAE at any time during the study
- Incidence of vaccine-type viral shedding
- Outcomes of pregnancies.

3.5 Analysis Populations

3.5.1 Efficacy Analysis Populations

Per Protocol Efficacy (PPE)

The PPE population will serve as the primary population for the evaluation of VE and for testing the primary and secondary efficacy hypotheses. To be eligible for inclusion in the PPE population, randomized study participants must satisfy the following criteria:

- CMV seronegative at Day 1 and CMV negative by PCR for non-vaccine strain virus from post Day 1 through Month 7
- Have received all 3 injections/vaccinations within the vaccination visit window specified in the SoA (Section 2)
- At any time from Day 1 through Month 7, did not have events, deviations from protocol, or engaged in activities that are deemed by the study Clinical Director to potentially interfere with the evaluation of efficacy or immune response to injections of V160.

Participants whose CMV status by PCR post Day 1 through Month 7 is not evaluable will be ineligible for inclusion in the PPE population. The categories of events, deviations from protocol, or activities that are deemed by the study Clinical Director to potentially interfere with the evaluation of efficacy or immune response to injections of V160 include the following:

1. Participant was not serologically confirmed as CMV seronegative (based on CMV IgG) during screening;
2. Participant was immunocompromised or had been diagnosed as having a congenital or acquired immunodeficiency, human immunodeficiency virus (HIV) infection, lymphoma, leukemia, systemic lupus erythematosus, rheumatoid arthritis, juvenile rheumatoid arthritis, inflammatory bowel disease, or other autoimmune condition at any time between Day 1 to Month 7;
3. Participant had previously received a non-study CMV vaccine.
4. Participant received systemic corticosteroids (equivalent ≥ 2 mg/kg total daily dose of prednisone or ≥ 20 mg/d for persons weighing >10 kg) for ≥ 14 consecutive days and has not completed treatment at least 30 days prior to any vaccination dose;

5. Participant received systemic corticosteroids exceeding physiologic replacement doses (approximately 5 mg/d prednisone equivalent) within 14 days prior to any vaccination dose;
6. Participant received any anti-viral agent with proven or potential activity against CMV (e.g. letermovir, ganciclovir, valganciclovir, foscarnet, cidofovir, valacyclovir) two weeks prior to any vaccination dose or likely to receive such an agent within two weeks after any vaccination dose.
7. Participant was receiving or has received in the year prior to randomization immunosuppressive therapies including but not limited to rapamycin (also sirolimus), tacrolimus (also FK-506 or Fujimycin), or other therapies used for solid organ/cell transplant, radiation therapy, immunosuppressive/cytotoxic immunotherapy, chemotherapy and other immunosuppressive therapies known to interfere with the immune response.
8. Participant used topical tacrolimus within 2 weeks before or after any vaccination dose;
9. Participant received study clinical material in a sequence that is different from the sequence corresponding to the vaccination group to which the participant was randomized into (i.e., incorrect vaccination sequence or cross-treatment).
10. Participant was administered improperly stored study clinical material that was deemed unacceptable for use.
11. Participant received improperly reconstituted study clinical material that may affect efficacy and/or safety.

Full Analysis Set (FAS)

The FAS will serve as a supportive analysis population for the evaluation of VE. The FAS population consists of all randomized participants who received at least 1 dose of the correct clinical material corresponding to the treatment regimen the participants were randomized into.

